### **6.2 Exclusion criteria**

Subjects are not permitted to enroll in the study if any of the following criteria is met:

1. Subject is receiving any investigational drugs or using any experimental devices in addition to LCM.
2. Subject meets the withdrawal criteria for SP0982 or is experiencing an ongoing serious adverse event (SAE).
3. Subject has an active suicidal ideation as indicated by a positive response (“Yes”) to either Question 4 or Question 5 of the “Since Last Visit” version of the Columbia-Suicide Severity Rating Scale (C-SSRS). The subject should be referred immediately to a Mental Healthcare Professional.
4. Subject has  $\geq$ 2x upper limit of normal (ULN) of any of the following: alanine aminotransferase (ALT), aspartate aminotransferase (AST), alkaline phosphatase (ALP), or  $>$ ULN total bilirubin ( $\geq$ 1.5xULN total bilirubin if known Gilbert’s syndrome). If subject has elevations only in total bilirubin that are  $>$ ULN and  $<$ 1.5xULN, fractionate bilirubin to identify possible undiagnosed Gilbert’s syndrome (ie, direct bilirubin  $<$ 35%).

For all subjects who entered EP0012 directly with a Baseline result  $>$ ULN for ALT, AST, ALP, or total bilirubin, a Baseline diagnosis and/or the cause of any clinically meaningful elevation must be understood and recorded in the eCRF.

Tests that result in ALT, AST, or ALP up to 25% above the exclusion limit may be repeated once for confirmation.

If the investigator has any doubts concerning the subject's eligibility, he/she should consult the UCB Study Physician or representative for clarification.

### 6.3 Withdrawal criteria

Subjects are free to withdraw from the study at any time, without prejudice to their continued care. Investigators should contact the Medical Monitor whenever possible to discuss the withdrawal of a subject in advance. All subjects discontinuing treatment with LCM for any reason should taper as described in Section 7.2. All subjects who withdraw due to an AE must be followed until resolution of the event or until the event is considered stable.

Subjects **must** be withdrawn from the study if any of the following events occur:

1. Tapered subjects from SP0982 who enter EP0012 after the 125th event will be withdrawn at the enrollment visit and enter directly into the Safety Follow-Up Period without and ET Visit being performed in EP0012.
2. The subject develops second or third degree atrioventricular (AV) block.
3. The subject becomes pregnant, as evidenced by a positive pregnancy test.
4. The sponsor or a regulatory agency requests withdrawal of the subject.
5. The subject is unwilling or unable to continue, or the legal representative is unwilling or unable to allow the subject to continue in the study.
6. In the case of liver function test (LFT) results of transaminases (ALT and/or aspartate AST)  $\geq 3x$  ULN to  $< 5x$ ULN and total bilirubin  $\geq 2x$ ULN or transaminases (AST and/or ALT)  $\geq 5x$ ULN, LCM must be immediately discontinued, and the subject withdrawn from the study. The LFTs will be repeated as soon as possible, and in no case more than 1 week later.
7. Subject  $\geq 6$  years of age has actual suicidal ideation since last visit as indicated by a positive response "Yes" to either Question 4 or Question 5 of the "Since Last Visit" version of the C-SSRS. The subject should be referred immediately to a Mental Healthcare Professional and must be withdrawn from the study.
8. Subject is unable to tolerate at least the minimum LCM target dose of 4mg/kg/day (oral solution) or 200mg/day (tablets).

Subjects **may** be withdrawn from the study if any of the following events occur:

- The subject requires a medication that is not permitted (see Section 7.8).
- The subject is unable to manage the completion of the diary, demonstrates a questionable diary, or is noncompliant with the study procedures or medications in the opinion of the investigator.
- An episode of status epilepticus, a prolongation of seizure duration, a worsening of seizure frequency, or emergence of a new seizure type considered by the investigator to require intervention.

- Subject develops a clinically relevant change in medical condition (or ECG or laboratory parameter) as determined by the investigator, and the investigator feels it is in the interest of the subject to withdraw.
- Discontinuation criteria for potential drug-induced liver injury (PDILI) are described in Section 6.3.1.

Investigators should attempt to obtain information on subjects in the case of withdrawal. For subjects considered as lost to follow up, the investigator should make an effort (at least 1 phone call and 1 written message to the subject), and document his/her effort (date and summary of the phone call and copy of the written message in the source documents), to complete the final evaluation. All results of these evaluations and observations, together with a narrative description of the reason(s) for removing the subject, must be recorded in the source documents. The electronic Case Report form (eCRF) must document the primary reason for withdrawal.

After the decision to withdraw the subject, the investigator will provide the subject with information about available alternative treatments.

### 6.3.1 Potential drug-induced liver injury IMP discontinuation criteria

Subjects with PDILI must be assessed to determine if investigational medicinal product (IMP) must be immediately and permanently discontinued. In addition, all concomitant medications and herbal supplements that are not medically necessary should also be discontinued.

The PDILI criteria below require immediate and permanent discontinuation of IMP:

- ALT or AST  $\geq 5xULN$
- ALT or AST  $\geq 3xULN$  and coexisting total bilirubin  $\geq 2xULN$

Subjects with ALT or AST  $\geq 3xULN$  who exhibit temporally associated symptoms of hepatitis or hypersensitivity. Hepatitis symptoms include fatigue, nausea, vomiting, right upper quadrant pain or tenderness. Hypersensitivity symptoms include fever (without clear alternative cause), rash, or eosinophilia (ie,  $>5\%$ ).

If a nondrug-related cause for the symptoms can be confirmed, these subjects may resume IMP administration after discussion with the responsible UCB physician, but only when the requirements for rechallenge with IMP as provided in Section 10.3.1.2.1 are followed.

The PDILI criterion below allows for subjects to continue on IMP at the discretion of the investigator.

- Subjects with ALT or AST  $\geq 3xULN$  (and  $\geq 2x$  Baseline) and  $< 5xULN$ , total bilirubin  $< 2xULN$ , and no eosinophilia (ie,  $\leq 5\%$ ), with no fever, rash, or symptoms of hepatitis (eg, fatigue, nausea, vomiting, right upper quadrant pain or tenderness).

Evaluation of PDILI must be initiated as described in Section 10.3.1. If subjects are unable to comply with the applicable monitoring schedule, IMP must be discontinued immediately. See Section 6.3 for when and how to discontinue subjects from the IMP. See Section 8.2 for the procedures to be performed at the time of discontinuation.

Investigators should attempt to obtain information on subjects in the case of IMP discontinuation to complete the final evaluation. Subjects with PDILI should not be withdrawn from the study until investigation and monitoring are complete. All results of these evaluations and observations, as well as the reason(s) for IMP discontinuation and subject withdrawal (if applicable), must be recorded in the source documents. The CRF must document the primary reason for IMP discontinuation.

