**Table 10–3: Required investigations and follow up for PDILI**

Laboratory value			Immediate		Follow up	
ALT or AST	Total bilirubin	Symptoms a of hepatitis or hypersensitivity	Consultation requirements	Actions	Testing	Evaluation
≥3xULN	≥2xULN b	NA	Hepatology consult. c	Immediate, permanent IMP discontinuation.	Essential: Must have repeat liver chemistry values and additional testing completed ASAP (see Section 10.3.1.3); recommended to occur at the site with HCP.	Monitoring of liver chemistry values at least twice per week until values normalize, stabilize, or return to within Baseline values. d
≥8xULN	NA	Medical Monitor must be notified within 24 hours (eg, by laboratory alert) and subject discussed with Medical Monitor ASAP.				
≥3xULN	NA	Yes				
≥3xULN (and ≥2x Baseline) and <5xULN	<2xULN	No	Discussion with Medical Monitor required if the criterion that allows for IMP continuation is met.	Further investigation – immediate IMP discontinuation not required (see Section 10.3.1.2).	Not required unless otherwise medically indicated (at discretion of investigator).	
≥5xULN (and ≥2x Baseline)	<2xULN	No	Discussion with Medical Monitor required.	Immediate, permanent IMP discontinuation.	Essential: Every attempt must be made to have repeat liver chemistry values and additional testing completed within 48 hours at the site with HCP (see Section 10.3.1.3).	Monitoring of liver chemistry values at least twice per week until values normalize, stabilize, or return to within Baseline values. d

---

ALP=alkaline phosphatase; ALT=alanine aminotransferase; ASAP=as soon as possible; AST=aspartate aminotransferase; HCP=healthcare practitioner; IMP=investigational medicinal product; NA=not applicable; PDILI=potential drug-induced liver injury; ULN=upper limit of normal

a Hepatitis symptoms include fatigue, nausea, vomiting, and right upper quadrant pain or tenderness; hypersensitivity symptoms include eosinophilia (>5%), rash, and fever (without clear alternative cause).

b If the subject also has  $\geq 2$ xULN ALP, the possibility of an indication of biliary obstruction should be discussed with the Medical Monitor.

c Details provided in [Section 10.3.1.1](#). The local hepatologist is the expert usually consulted by the treating physician for assessment and management of potential hepatic disease. This would usually be a hepatologist, but may be a gastroenterologist.

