#### 10.3.1.2.1 IMP restart/rechallenge (if applicable)

Rechallenge with a substance potentially causing drug-induced liver injury is dangerous, may be fatal, and must not occur.

Subjects who are immediately discontinued from IMP due to having met certain criteria for PDILI (as described in Section 6.3.1 and Table 10-3), but for whom an alternative diagnosis is confirmed, can rarely restart IMP. Rechallenge with IMP can occur only if ALL of the following requirements are met:

- The results of additional testing and monitoring described in Section 10.3.1.3 and Section 10.3.1.4 confirm a nondrug-related cause for the abnormal hepatic laboratory parameters and any associated symptoms (ie, a subsequent alternative diagnosis fully explains the hepatic findings).
- No alternative treatment options are available to the subject.
- The subject has shown clear therapeutic benefit from the IMP.
- Subject's ALT or AST elevations do not exceed  $\geq 3xULN$ .
- Subject's total bilirubin is  $<1.5xULN$ .
- Subject has no signs or symptoms of hypersensitivity.
- The rechallenge is approved by the UCB responsible physician and a hepatologist. The hepatologist must be external to UCB. It is recommended that the hepatologist be a local hepatology expert or the hepatologist treating the subject.

Subject agrees to the investigator-recommended monitoring plan.

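### For identical liver values, Section 6.3 criterion 6 orders withdrawal from the study, while Section 6.3.1 defers withdrawal and Section 10.3.1.2.1 keeps a conditional restart open

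*Protocol*

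**What the plan says.** Protocol Section 6.3 has a list of events after which a subject must be withdrawn. Criterion 6 in that list applies to ALT and/or AST from 3 to below 5 times ULN with total bilirubin at least 2 times ULN, or ALT and/or AST at least 5 times ULN. The instruction is "LCM must be immediately discontinued, and the subject withdrawn from the study", followed by "The LFTs will be repeated as soon as possible, and in no case more than 1 week later".

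Section 6.3.1, on potential drug-induced liver injury (PDILI), names ALT or AST at least 5 times ULN, or at least 3 times ULN with bilirubin at least 2 times ULN. It introduces them with "The PDILI criteria below require immediate and permanent discontinuation of IMP". On study status it says "Subjects with PDILI should not be withdrawn from the study until investigation and monitoring are complete".

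Table 10–3 sets the work-up by row. For ALT or AST at least 5 times ULN (and at least 2 times Baseline), bilirubin below 2 times ULN and no symptoms, it says "Every attempt must be made to have repeat liver chemistry values and additional testing completed within 48 hours". For the stopping rows with raised bilirubin, with ALT or AST at least 8 times ULN, or with symptoms, it asks for the repeat as soon as possible and sets no hour limit. After that comes "Monitoring of liver chemistry values at least twice per week until values normalize, stabilize, or return to within Baseline values", unless another schedule is agreed.

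Section 10.3.1 makes the stop permanent unless another diagnosis fully explains the findings. Section 10.3.1.2.1 says that subjects stopped for PDILI "but for whom an alternative diagnosis is confirmed, can rarely restart IMP", and only if every listed condition is met.

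**The concern.** A site faced with these values cannot both withdraw the subject now and keep the subject in the study until the work-up is finished. If the protocol does not settle this, two sites can handle the same event differently and both be compliant with part of the text.

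Two things depend on it. One is the delivery of the repeat testing and aetiology work-up as study procedures in cases that include potential Hy's Law events. The other is a primary safety variable in Section 4.1.1, subject withdrawals due to treatment-emergent adverse events: the same event may be an immediate withdrawal at one site and a drug stop with continued participation at another.

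**Working it through.** No figure in the plan needs reproducing. The check sets the current texts side by side.

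**1. Are the values the same?** Let a be the ALT/AST multiple of ULN and b the bilirubin multiple.
- Criterion 6: {3 ≤ a < 5 and b ≥ 2} or {a ≥ 5}.
- Section 6.3.1: {a ≥ 5} or {a ≥ 3 and b ≥ 2}.
- Split the last set: {a ≥ 3 and b ≥ 2} = {3 ≤ a < 5 and b ≥ 2} or {a ≥ 5 and b ≥ 2}. The second part already lies inside {a ≥ 5}.

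The two trigger sets are therefore identical. A grid of values from 2.9 to 12 times ULN for ALT/AST and 1 to 3 times ULN for bilirubin agreed in every cell.

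**2. What follows from the trigger?**

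| Point | 6.3 criterion 6 | PDILI text |
|---|---|---|
| Study drug | Stop at once | Stop at once, permanently unless another diagnosis explains the findings (6.3.1, 10.3.1) |
| Study status | Withdraw | Do not withdraw until investigation and monitoring are complete (6.3.1) |
| Repeat test | As soon as possible, at most 1 week | 48-hour target in one row; as soon as possible in the other stopping rows (Table 10–3) |
| Later monitoring | Silent | At least twice weekly unless otherwise agreed (Table 10–3) |
| Restart | Closed by withdrawal | Rare and conditional (10.3.1.2.1) |

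The study-status row is a direct contradiction. The restart row follows from it: the alternative diagnosis comes out of the work-up, so withdrawal at the trigger closes the route before the diagnosis can be made.

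**3. Do the cross-references settle it?** No. Section 6.3.1 sends the reader to 6.3 for when and how to discontinue the drug. Section 6.3 points to 6.3.1, but from the list of reasons for which a subject may be withdrawn, whereas criterion 6 stands in the list that requires withdrawal. The references run in a circle.

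**4. How large is the timing mismatch?** In the single row with an hour target, 1 week = 7 × 24 = 168 hours, against 48 hours: 168/48 = 3.5. This compares an outer bound with a best-effort target, and a repeat within 48 hours satisfies both texts.

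**5. Is follow-up still required after withdrawal?** Yes. Section 6.3 itself requires subjects withdrawn for an adverse event to be followed to resolution or stability. Section 10.3.1 makes every PDILI event a reportable adverse event. Section 10.1.3 applies the follow-up rule and refers to 10.3.1.4, which continues monitoring until values normalize, stabilize or return to Baseline. Section 10.3.1.2 requires testing and monitoring for all PDILI events. Section 10.1.3 adds only that follow-up usually runs for 30 days after the drug is stopped.

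**6. What is one case worth in the primary variable?** Sections 1 and 5.1.2 plan up to 250 subjects. One case counted differently moves the proportion by 1/250 = 0.4 percentage points, and by more if the denominator is smaller.

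**The case against.** The strongest reply is that little is at stake. Three stronger readings are tempting, and the documents do not support them.

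- **Lost follow-up.** A reader might infer that withdrawal under criterion 6 leaves the worst liver cases with one sample and no aetiology work-up. Sections 6.3, 10.1.3, 10.3.1, 10.3.1.2 and 10.3.1.4 all continue to require follow-up. Criterion 6 is silent on later sampling, and silence does not displace Table 10–3, so counting one guaranteed sample against two is not a fair comparison.
- **A 3.5-fold delay in the most serious cases.** The 48-hour target belongs to the row with ALT or AST at least 5 times ULN, bilirubin below 2 times ULN and no symptoms. The rows with raised bilirubin or symptoms carry no hour limit and agree with criterion 6.
- **Inconsistent handling of symptomatic subjects.** Table 10–3 calls the stop permanent and 6.3.1 allows a resumption, but 10.3.1 largely reconciles the two through its exception for a confirmed alternative diagnosis.

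It can also be said that Section 12.3.1 summarizes adverse events leading to discontinuation of study drug, which would capture a liver stop whatever the study status, and that counting rules belong to the SAP. That is fair as far as it goes. The primary variable in 4.1.1 is nevertheless worded as subject withdrawals, and the protocol treats withdrawal and drug discontinuation as separate acts with separately recorded reasons (6.3 and 6.3.1). An SAP can choose how to count recorded statuses; it cannot make sites assign the same status when their instructions conflict.

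None of this removes the contradiction on study status.

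**Conclusion.** The protocol is wrong as written on one central point: for identical liver values it orders withdrawal in one section and defers it in the next, with no rule of precedence. The conflict over restart follows from that. The repeat-test mismatch is secondary and confined to one row of Table 10–3.

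The consequence is inconsistent study status between sites, not lost follow-up. Delivery of the in-study monitoring and work-up may vary. In the primary withdrawal variable, a subject who stays in or restarts is counted differently from one withdrawn at the trigger; a subject who is withdrawn later, after the work-up, differs only in date.

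The number of affected subjects is not given and cannot be derived. The 0.4 percentage points per case assume a denominator of 250. The effect on the reported count also assumes that the variable is derived from study withdrawal, as 4.1.1 words it; if it is derived from drug discontinuation, the count would be less affected. The contradiction itself rests on no assumption.

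**What to change.** Reconcile Section 6.3 (criterion 6 and the reference to 6.3.1 in the list of optional withdrawals), Section 6.3.1, Section 10.3.1, Table 10–3 and Section 10.3.1.2.1, so that the protocol holds one statement on each of three matters:

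- the subject's study status after a liver stop, including when any withdrawal takes effect;
- the outer limit for the repeat test;
- whether restart is possible, and for which subjects.

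The cross-references should then lead to those statements, so that such cases enter the primary withdrawal variable in the same way at every site. Which clinical rule applies is for the sponsor to decide; this review does not prefer one.

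The cost is protocol wording and notice to sites. No new assessment is needed, because the tests are already listed in Tables 10–3 and 10–4.

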## 7 STUDY TREATMENT(S)

### 7.1 Description of investigational medicinal product(s)

Investigational medicinal product (IMP) will be provided as LCM oral solution (LCM 10mg/mL) and LCM tablets (LCM 50mg and LCM 100mg).

The oral solution formulation contains 10mg/mL of drug substance and is colorless to pale yellow in appearance.

The tablet formulation will be supplied in doses of 50mg and 100mg. The 50mg tablets are light pink, oval, film-coated tablets debossed with “SP” on 1 side and “50” on the other. The 100mg tablets are dark yellow, oval, film-coated tablets debossed with “SP” on 1 side and “100” on the other.

### 7.2 Treatment(s) to be administered

Lacosamide will be orally administered bid (at approximately 12-hour intervals in the morning and in the evening) in 2 equally divided doses (oral solution for pediatric subjects weighing <50kg or tablets for adult subjects [ $\geq 18$  years of age] and pediatric subjects [ $< 18$  years of age] weighing  $\geq 50$ kg); during the study, subjects who initially started on oral solution may transfer to tablets at the investigator’s discretion.

Tablets **must not be broken**. In rare cases where uneven dosing (e.g., 350mg/day, 450mg/day, 550mg/day, etc) is medically needed, although the interactive response technology (IRT) will not dispense the exact dose, please contact the Medical Monitor for additional instructions. If subjects are taking an odd number of tablets per day, (eg, 7 tablets totaling 350mg), they should take the lower dose in the morning (eg, 150mg [3 tablets]) and the higher dose in the evening (eg, 200mg [4 tablets]).

During the study, investigators will be allowed to increase or decrease the dose of LCM to optimize tolerability and seizure reduction for each subject, within the dose range described in [Table 7-1](#).

#### 7.2.1 Treatment Period

At Visit 1, subjects who completed SP0982 will start on a dose of LCM 10mg/kg/day for pediatric subjects weighing <30kg, LCM 8mg/kg/day for pediatric subjects weighing  $\geq 30$ kg to <50kg, and LCM 400mg/day (200mg bid) for adult subjects ( $\geq 18$  years of age) or pediatric subjects weighing  $\geq 50$ kg. Subjects who are eligible Baseline failures from SP0982 will start at Visit 1 on a dose of LCM 2mg/kg/day for pediatric subjects weighing <50kg, and LCM 100mg/day (50mg bid) for adult subjects ( $\geq 18$  years of age) or pediatric subjects weighing  $\geq 50$ kg.

Baseline failures are required to complete Week 1 of dosing before LCM dosing flexibility based on tolerability is allowed. Investigators will assess whether a subject would tolerate a further LCM dose increase or whether a subject should hold the dose for a longer duration. There is no limit to the number of back titration steps or dose holds allowed and all are at the Investigator's discretion; however, subjects must achieve the minimum LCM target dose of 4mg/kg/day (oral solution) or 200mg/day (tablets).

Subjects who tapered in SP0982 after the 125th event will enroll at Visit 1 and proceed directly to the Safety Follow-up Period without receiving LCM.

At any time during the course of the study if it becomes apparent that a subject is unable to attain at least this minimum dose of 4mg/kg/day (oral solution) or 200mg/day (tablets), then the subject must enter the Taper Period and be withdrawn from the study.

During EP0012, investigators will be allowed to increase or decrease the dose of LCM to optimize tolerability and seizure reduction. Lacosamide doses may be increased or decreased in steps of no more than 2mg/kg/day (oral solution) or 100mg/day (tablets). Subjects must remain on the dose for  $\geq 7$  days before a subsequent dose escalation.

Table 7-1 provides the minimum and maximum LCM dose during the Treatment Period.

